6.1. Screening

For screening procedures see the [Schedule Of Activities](#) and [ASSESSMENTS](#) sections. Screening is to be performed within 28 days of registration. For medical history, include history of other diseases (active or resolved) and concomitant illnesses.

6.2. Study Period

For treatment period procedures, see the [Schedule Of Activities](#) and [ASSESSMENTS](#) sections. The End of Treatment assessments are to be performed approximately 28 days after the last dose of study drug. Obtain these assessments if not completed during the previous week on study (during the previous 6 weeks on study for tumor assessments).

Patients whose disease has not progressed at the end of treatment will enter into disease follow-up. During this follow-up period, patients will have disease assessments performed every 12 weeks \pm 7-days. Once patients have exhibited disease progression or began a new anti-cancer therapy (not including radiotherapy to a non-target tumor), whichever occurs first, the date of progression will be recorded on the appropriate CRF page and they will be withdrawn from the study. No further data will be collected from these patients. Patients continuing to experience treatment-related toxicity following discontinuation of study treatment will continue to be followed at least every 4 weeks until resolution or determination, in the clinical judgment of the Investigator, that no further improvement is expected.

For follow-up procedures see [Schedule Of Activities](#).

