- a. Dose escalation and de-escalation of PF-05082566 follows the Time-to-Event Continual Reassessment Method (TITE-CRM) up to a maximum dose of 5.0 mg/kg q3wk.
- b. The MTD is defined as the highest combination dose with a DLT rate <25% from the model estimate.
- c. Dose escalation stops if:
 - Maximum study sample size is reached; or
 - 9 evaluable patients have been treated at the estimated MTD; or
 - All doses appear to be overly toxic and the MTD cannot be determined in the current trial.

Treatment with study drugs will continue until completion of 32 cycles (approximately 24 months) of treatment, disease progression (RECIST v. 1.1), patient refusal, unacceptable toxicity occurs, or the study is prematurely terminated by the Sponsor; whichever comes first. Discontinuation from treatment may be considered at the investigator's discretion for patients who have attained a confirmed CR, have been treated for at least 24 weeks on study, and have at least two treatments with MK-3475 and PF-05082566 beyond the date the initial CR was declared. Patients who then experience radiologic disease progression will be eligible for re-treatment with both study drugs at the discretion of the investigator and by the approval of the Sponsor, if no cancer treatment was administered since the last dose of study

drugs, the patient meets the safety parameters listed in the Inclusion/Exclusion criteria, and the trial is still open. Patients will resume therapy at the same dose and schedule at the time of initial discontinuation. Patients who complete a maximum number of 32 cycles (approximately 24 months) on study treatment and demonstrate clinical benefit with manageable toxicity and are willing to continue receiving the study treatment will be given the opportunity to continue treatment upon agreement between investigator and sponsor.

Dose Escalation Criteria:

Based on the starting dose example above, dose escalation and de-escalation will be carried out according to Table 1.

Table 1. Dose Escalation Cohorts

Dose Escalation Cohort	PF-05082566	MK-3475
-1	0.20 mg/kg q3wks	2 mg/kg q3wks
1 (Starting Dose Level)	0.45 mg/kg q3wks	2 mg/kg q3wks
2	0.9 mg/kg q3wks	2 mg/kg q3wks
3	1.8 mg/kg q3wks	2 mg/kg q3wks
4	3.6 mg/kg q3wks	2 mg/kg q3wks
5	5 mg/kg q3wks	2 mg/kg q3wks

* q3wks: every 3 weeks

SCHEDULE OF ACTIVITIES:

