32. **Follow Up:** Patients should be evaluated up to 90 days after last dose of study treatment. Refer to the protocol for specific guidelines. Patients continuing to experience toxicity following discontinuation of study treatment will continue to be followed at least every 4 weeks until resolution or determination, in the clinical judgment of the Investigator, that no further improvement is expected. PK and immunogenicity samples should be collected as described in the PK and Immunogenicity Assessment section in Schedule of Activities ([Table 3](#)). Patients whose disease has not progressed at the end of treatment will enter into disease follow-up. During this follow-up period, patients will have disease assessments performed every 12 weeks \pm 7-days. Once patients have exhibited disease progression or began a new anti-cancer therapy, or 6-month follow-up from the date of the first dose of the last enrolled patient, whichever occurs first, they will be withdrawn from the study. See [Section 4.3.1](#) Contraception for guidelines on contraception checks during this period.
33. **De novo tumor biopsy for biomarker assessment (Dose escalation):** For patients in dose-escalation cohorts, unscheduled optional de novo tumor biopsies may be collected at the discretion of the investigator and sponsor to support the assessment of disease progression.
34. **De novo tumor biopsy for biomarker assessment (Expansion cohorts):** Mandatory for patients in expansion cohorts only. A de novo biopsy will be required at study entry followed by a second biopsy at the time of the Week 9 scans (after 3 cycles of treatment).
35. **Continued Treatment Beyond Cycle 8:** This will be on a reduced visit schedule (Day 1 of each cycle), or as clinically indicated.
36. **Thyroid Function Tests:** To be collected every 2 cycles for the first 8 cycles, and then every 4 cycles (Cycles 1, 3, 5, 7, 11, 15 etc.).
37. **Hepatitis B and C Tests:** Conduct tests for hepatitis B surface antigen, core antibody, and anti-hepatitis C. Other tests may be conducted per standard practice to confirm an active hepatitis infection.

Table 4. Required Laboratory Tests

SAFETY LABORATORY REQUIREMENTS	
Refer to the Schedule of Activities table for specific timepoints and instructions	
Assessments	
Hematology Panel:	Chemistry Panel:
Absolute Neutrophil Count	Sodium
Hemoglobin	Potassium
	Total Calcium
Platelet Count	Creatinine
WBC with differential (5-part if available)	Albumin

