Discontinuation from treatment may be considered at the investigator's discretion for patients who have attained a confirmed complete response (CR), that have been treated for at least 24 weeks on study, and have at least two treatments with MK-3475 and PF-05082566 beyond the date the initial CR was declared. Patients who then experience radiologic disease progression will be eligible for treatment with both study drugs at the discretion of the investigator and by the approval of the Sponsor, if no cancer treatment was administered since the last dose of study drugs, the patient meets the safety parameters listed in the Inclusion/Exclusion criteria, and the trial is open. Patients will resume therapy at the same dose and schedule at the time of initial discontinuation. Patients who complete a maximum number of 32 cycles (approximately 24 months) on study treatment and demonstrate clinical benefit with manageable toxicity and are willing to continue receiving the study treatment will be given the opportunity to continue treatment upon agreement between investigator and sponsor.

CCI

In addition, patients with RECIST defined disease progression who are continuing to derive clinical benefit from the study treatment will be eligible to continue treatment with PF-05082566 plus MK-3475 provided that the treating physician has determined that the benefit/risk for doing so is favorable. (Refer to [Section 5.3.4](#) and [Section 7.4.1](#) for details). Also in this case, the maximum period on-treatment will be 32 cycles (approximately 24 months).

[figure not shown]
After estimation of the MTD for the combination on the q3wk schedule, PF-05082566 may be co-administered along with MK-3475 to study safety and tolerability on an alternative dosing schedule for both drugs. Other study drug doses may also be tested based on emerging safety and tolerability data. The initiation of additional patient cohorts to explore

additional dosing schedules or study drug doses will be done at the discretion of the Sponsor, and can occur in parallel with enrollment of patients in expansion cohorts on the q3wk dosing schedule.

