5.3.3. Treatment Duration

The study begins when the first patient signs the informed consent.

The treatment duration with both study drugs is 32 cycles (approximately 24 months) calculated from the date of the first combined doses of PF-05082566 and MK-3475. Patients may continue on treatment with both agents until disease progression (RECIST v. 1.1),

patient refusal, unacceptable toxicity occurs, or the study is prematurely terminated by the Sponsor; whichever comes first (see [Section 6.3](#) for Patient Withdrawal).

Discontinuation from treatment may be considered at the investigator's discretion for patients who have attained a confirmed CR, that have been treated for at least 24 weeks on study, and have at least two treatments with MK-3475 and PF-05082566 beyond the date the initial CR was declared. Patients who then experience radiologic disease progression will be eligible for re-treatment with both study drugs at the discretion of the investigator and by the approval of the Sponsor, if no cancer treatment was administered since the last dose of study drugs, the patient meets the safety parameters listed in the Inclusion/Exclusion criteria, and the trial is still open. Patients will resume therapy at the same dose and schedule at the time of initial discontinuation.

Patients who complete a maximum number of 32 cycles (approximately 24 months) on study treatment and demonstrate clinical benefit with manageable toxicity and are willing to continue receiving the study treatment will be given the opportunity to continue treatment upon agreement between investigator and sponsor.

CCI

A large rectangular area of the document is redacted with a solid black box.

CCI

A large rectangular area of the document is redacted with a solid black box.A rectangular area of the document is redacted with a solid black box.

■ 

A line of text is partially redacted with a solid black box.

■ 

A line of text is partially redacted with a solid black box.

■ 

A line of text is partially redacted with a solid black box.

- CCI [REDACTED]

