5.6.1. Prohibited Concomitant Medications

Medications or vaccinations specifically prohibited in the exclusion criteria are not allowed during the ongoing trial, except in the case of hematopoietic growth factors and the use of steroids for symptomatic treatment. If there is a clinical indication for one of these or other medications or vaccinations specifically prohibited during the trial, discontinuation from trial therapy or vaccination may be required. The investigator should discuss any questions regarding this with the Sponsor Clinical Director and/or Medical Monitor. The final decision on any supportive therapy or vaccination rests with the investigator and/or the patient's primary physician. However, the decision to continue the patient on trial therapy or

vaccination schedule requires the mutual agreement of the Investigator, the Sponsor, and the patient.

Patients are prohibited from receiving the following therapies during the Screening and Treatment Phase (including retreatment for post-complete response relapse) of this trial:

- Anti-cancer systemic chemotherapy or biological therapy.
- Immunotherapy not specified in this protocol.
- Chemotherapy.
- Investigational agents other than MK-3475 or PF-05082566.
- Radiation therapy.

Note: Radiation therapy to a symptomatic solitary lesion or to the brain may be allowed after consultation with Sponsor.

- Live vaccines.
- Glucocorticoids for any purpose other than to modulate symptoms from an event of clinical interest of suspected immunologic etiology, except as agreed upon by the Sponsor.

Consider withholding or discontinuing concomitant therapy with monoclonal antibodies of the same subclass as the study drugs (ie, IgG2 and IgG4), in patients where anti-drug antibodies are detected while on-study.

The concurrent use of vitamins or herbal supplements should be considered with caution.

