6.3. Patient Withdrawal

Patients may withdraw from treatment at any time at their own request, or they may be withdrawn at the discretion of the investigator or sponsor for safety or behavioral reasons, or the inability of the patient to comply with the protocol-required schedule of study visits or procedures at a given study site.

Reasons for discontinuation of study treatment may include:

- Confirmed objective disease progression according to RECIST version 1.1 (see the Study Design [Section 3](#) for details and exceptions);
- Global deterioration of health status requiring discontinuation;
- Unacceptable toxicity (possibly associated with both study drugs);
- Pregnancy;
- Significant protocol violation;
- Lost to follow-up;
- Patient refused further treatment;
- Study terminated by Sponsor;
- Death.

Reasons for withdrawal from study follow-up may include:

- Completed study follow-up;
- Study terminated by Sponsor;
- Lost to follow-up;
- Death.

If a patient does not return for a scheduled visit, every effort should be made to contact the patient. All attempts to contact the patient and information received during contact attempts must be documented in the patient's medical record. In any circumstance, every effort should be made to document patient outcome, if possible. The investigator should inquire about the reason for withdrawal, request the patient to return for a final visit, if applicable, and follow-up with the patient regarding any unresolved AEs.

If the patient refuses further visits, no further study specific evaluations should be performed, and no additional data should be collected. The sponsor may retain and continue to use any data collected before such withdrawal of consent.

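### Post-CR re-treatment opens at the same progression that withdraws a follow-up patient, and the SAP then counts the elective drug-free gap as treatment time and as a dose delay

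*Protocol*

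**What the plan says.** **Re-treatment is allowed.** A patient in confirmed CR who has been treated for at least 24 weeks, with at least two treatments after the CR was first declared, may stop. On later progression the Protocol Summary makes that patient "eligible for re-treatment with both study drugs at the discretion of the investigator and by the approval of the Sponsor". Section 3.1 says "Patients who then experience radiologic disease progression will be eligible for treatment with both study drugs", and Section 5.3.3 says "Patients who then experience radiologic disease progression will be eligible for re-treatment with both study drugs at the discretion of the investigator". The conditions are no intervening cancer treatment, the safety entry criteria met, and the trial still open. Dose and schedule are those at the time of stopping. Section 5.6.1 counts this as part of the Treatment Phase ("including retreatment for post-complete response relapse) of this trial").

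**Withdrawal at the same event.** Under Section 6.2 a patient who has not progressed at end of treatment enters disease follow-up. At progression or new anti-cancer therapy, "they will be withdrawn from the study. No further data will be collected from these patients". Footnote 32 has the same trigger ("Once patients have exhibited disease progression or began a new anti-cancer therapy") and adds a limit of six months from the last enrolled patient's first dose.

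**SAP.** It mentions neither re-treatment nor a planned break.
- On-treatment period (3.5.1, 5.2.7): one window, from first dose to 30 days after last dose, or to the day before new anti-cancer drug therapy if earlier.
- Cycle end (6.5.3): the day before the next cycle starts.
- Intended duration, exposure duration and the DI/RDI denominator (6.5.3.1, 6.5.3.2): first dose to the end of the last dosed cycle, with nothing subtracted.
- Dose delay (6.5.3.4): deviation from the planned day, set relative to the previous administration.

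**The concern.** The event that opens re-treatment is the event that ends participation. A site cannot follow both rules as written, and the visible text does not say which prevails.

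If Section 6.2 were followed literally, scheduled visits and laboratory tests during re-exposure would not be collected. SAEs and events of clinical interest would still be reported, because their 90-day windows are tied to the last dose or to the end of treatment (Sections 8.2 and 7.1.2.1).

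If re-treatment is recorded, as is likely, a patient who received every planned dose appears in the tables with low RDI, a long treatment duration and a delay that was in fact an elective stop. The safety tables also lose comparability. SAEs and events of clinical interest from day 31 to day 90 after the first course would be summarised as on-treatment for a patient re-treated after that. For an otherwise identical patient who is not re-treated, they would only be listed and flagged.

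**Working it through.** **Inputs from the documents.** Dosing is every 21 days. The 24-week minimum before a CR stop equals 8 cycles. The formulas are those of SAP 5.2.7, 6.5.3.1, 6.5.3.2 and 6.5.3.4.

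**Assumed inputs; the documents give none.** Eight doses before the stop and eight after, all full and on time. The gap is G weeks, counted from the end of the last initial 21-day cycle, with G = 12, 24 or 52.

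**Check against the SAP's own example.** In 6.5.3.4 a dose on Day 1 makes Day 22 the planned day, and Day 23 or 24 is no delay. Delay = (day of dose − day of previous dose) − 21 gives 0, 1 and 2 days for Days 22, 23 and 24. All are in the no-delay category, so the formula is read correctly.

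**Formulas for a re-treated patient**
- Last initial dose: day 1 + 7 × 21 = 148.
- First re-treatment dose: day 148 + 21 + 7G. Last dose: 147 days later.
- Intended duration = exposure duration = 24 + G + 24 weeks.
- RDI = 100 × 16 / (duration / 3) = 100 × 48 / (48 + G).
- Delay = (21 + 7G) − 21 = 7G days.
- On-treatment period as written: day 1 to last dose + 30.
- Two separate windows: 2 × (148 + 30) = 356 days.

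| G (weeks) | Duration (weeks) | RDI | Delay (days) | On-treatment as written (days) | Excess over 356 (days) |
|---|---|---|---|---|---|
| 12 | 60 | 48/60 = 80.0% | 84 | 400 + 30 = 430 | 74 |
| 24 | 72 | 48/72 = 66.7% | 168 | 484 + 30 = 514 | 158 |
| 52 | 100 | 48/100 = 48.0% | 364 | 680 + 30 = 710 | 354 |

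The dosed time is 48 weeks in every row. Under the SAP's cycle-end rule the last cycle before the break lasts 3 + G weeks: 15, 27 or 55.

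**Check of the remedy.** If each course ends with the 21-day cycle of its last dose, duration is 24 + 24 = 48 weeks and RDI = 48/48 = 100%. If the gap were cut only after the 30-day safety tail, the first course would keep 30 − 20 = 10 extra days and RDI would be 336/346 = 97.1%. The safety window and the exposure window therefore need separate end points.

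**What does not change.** The DLT window is the first two cycles. PFS and duration of response end at first progression or death. All of these precede re-treatment.

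**The case against.** **Re-treatment clearly prevails.** It is granted in three places, Section 5.6.1 puts it in the Treatment Phase, and checking the entry safety criteria requires laboratory results. A specific provision normally governs a general end-of-follow-up sentence. This stands. A reader might infer that re-exposure data will be lost, but the documents taken together do not support that. What is missing is an exception, not permission.

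**Redaction.** Blacked-out text follows the re-treatment paragraphs in 3.1 and 5.3.3, and Section 5.3.4, on treatment after radiologic progression, is hidden. An exception could sit there, so the claim is limited to the visible text. The pointer to exceptions in Section 6.3 does not help: it qualifies a reason for stopping treatment ("Confirmed objective disease progression according to RECIST version 1.1 (see the Study Design"), not withdrawal from the study.

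**Dose delay.** After an elective stop, no dose is planned 21 days later, so a programmer might not score a delay. That is sensible, but the SAP sets the planned day relative to the previous administration and makes no allowance for a planned stop.

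**Elapsed time is a defined result.** The formulas do return a value, and splitting courses is a convention. But the denominator is named intended duration, and no dosing was intended during the gap.

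**Few patients.** This stands. A patient must reach confirmed CR, stop, progress without other treatment, and be approved while the trial is open. The dosing listing planned in SAP 6.5.3 would show the gap; the summary tables would not.

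**Conclusion.** The point holds as a minor one. The protocol lacks an exception in two places. The SAP's stated rules, not merely its silence, give misleading exposure, delay and on-treatment summaries for any re-treated patient. The size is illustrative: RDI of 80.0% and 48.0% for 12- and 52-week gaps, against 100% once the gap is excluded, with delays of 84 and 364 days. These figures rest on the assumed 8 + 8 full, on-time doses and on the view that an elective stop is not intended treatment time.

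A reader might infer a worst case from "The treatment duration with both study drugs is 32 cycles (approximately 24 months) calculated from the date of the first combined doses". The documents set no such calendar limit on the gap. Section 5.3.3 counts cycles, says only approximately 24 months, and allows continuation by agreement. The 104 weeks in SAP Section 2 is a data cut-off counted from the last patient's first dose. What does restrict long gaps is footnote 32. With six months taken as 26 weeks, a 52-week gap after 24 weeks of treatment requires enrolment at least 24 + 52 − 26 = 50 weeks before the last patient.

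Only descriptive exposure and safety summaries for a few patients are affected. DLT/MTD, PFS and duration of response are not.

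**What to change.** **Protocol, Section 6.2 and footnote 32.** Add one sentence to each: patients approved for post-CR re-treatment under Sections 3.1 and 5.3.3 are not withdrawn at that progression and return to the treatment-period Schedule of Activities.

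**SAP.** Add one rule for both drugs: re-treatment is a second course.
- *Safety:* the on-treatment period becomes two windows, each ending 30 days after that course's last dose, or the day before new anti-cancer drug therapy if earlier.
- *Exposure:* for cycle duration, exposure duration, DI/RDI and dose delays, each course ends 21 days after its last dose, and the time until the first re-treatment dose is excluded. SAP 6.5.3 now closes a patient's last cycle at 28 days, so the rule should say that 21 applies.

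**Cost.** Two protocol sentences, one SAP rule referenced from 3.5.1, 5.2.7, 6.5.3, 6.5.3.1, 6.5.3.2 and 6.5.3.4, and ordinary treatment-period data collection for the few re-treated patients. The decision to offer re-treatment stays with the investigator and sponsor.

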6.3. Patient Withdrawal

Patients may withdraw from treatment at any time at their own request, or they may be withdrawn at the discretion of the investigator or sponsor for safety or behavioral reasons, or the inability of the patient to comply with the protocol-required schedule of study visits or procedures at a given study site.

Reasons for discontinuation of study treatment may include:

- Confirmed objective disease progression according to RECIST version 1.1 (see the Study Design [Section 3](#) for details and exceptions);
- Global deterioration of health status requiring discontinuation;
- Unacceptable toxicity (possibly associated with both study drugs);
- Pregnancy;
- Significant protocol violation;
- Lost to follow-up;
- Patient refused further treatment;
- Study terminated by Sponsor;
- Death.

Reasons for withdrawal from study follow-up may include:

- Completed study follow-up;
- Study terminated by Sponsor;
- Lost to follow-up;
- Death.

If a patient does not return for a scheduled visit, every effort should be made to contact the patient. All attempts to contact the patient and information received during contact attempts must be documented in the patient's medical record. In any circumstance, every effort should be made to document patient outcome, if possible. The investigator should inquire about the reason for withdrawal, request the patient to return for a final visit, if applicable, and follow-up with the patient regarding any unresolved AEs.

If the patient refuses further visits, no further study specific evaluations should be performed, and no additional data should be collected. The sponsor may retain and continue to use any data collected before such withdrawal of consent.

